5 STUDY ENROLLMENT AND WITHDRAWAL

5.1 Subject Inclusion Criteria

To be eligible to participate in this study, an individual must meet all of the following criteria:

- Provide signed and dated informed consent form;
- Male or female, aged 18 to 65 (inclusive);
- tDCS naïve; and
- Willing to comply with all study procedures and be available for the duration of the study.

In addition, **TMD subjects** must qualify as:

- Diagnosed with chronic TMD as defined by the Diagnostic Criteria (DC) for TMD and the American Academy of Orofacial Pain (DC/TMD)³⁶:
“Chronic TMD pain and dysfunction for at least one year from the clinical exam session (DC/TMD: Masticatory myofacial pain with/without referral) not adequately controlled by previous therapies (eg, NSAIDs, muscle relaxants)”
- TMJ open-surgery naïve;
- TMD maximum pain score pain of greater than or equal to 3 (moderate to severe) on a 0-10 VAS, despite existing treatment, for 3 days in the 7 days preceding study consent, based on report at the screening session;
- If taking pain medications, the dose regimen must be stable for at least 4 weeks prior to screening; and
- Willing to halt the introduction of new medications for chronic TMD symptoms during the study.

Emphasis is therefore placed on generalizability and chronicity of symptoms.

OR

To qualify as a **Healthy Volunteer**, subjects must be:

- Without self-reported history of systemic disorders or other chronic pain disorders, including migraine.

5.2 Subject Exclusion Criteria

An individual who meets any of the following criteria will be excluded from participation in this study:

- Existence of chronic pain disorder(s) other than TMD
- VAS rating lower than 3 during Screening Visit (week -3)
- History of a traumatic brain injury
- History or current evidence of a psychotic disorder (e.g. schizophrenia) or substance abuse (self-reported)
- Bipolar or severe major depression, as evidenced by a Beck Depression Inventory³⁷ score of ≥ 30
- Ongoing, unresolved disability litigation (self-reported)
- History of neurological disorder (e.g. epilepsy, stroke, neuropathy, neuropathic pain; self-reported)
- Opioid pain medications taken within the past 3 months
- Past allergic response to opioids or chemically related drugs (e.g., carfentanil)
- Excluded by MRI Center or PET Center safety screening checklist (as administered by study staff)
- Drug test positive for opioid or recreational drug (e.g., cannabis) at the time of the PET scan visits
- Pregnant or lactating (negative urine pregnancy test must be available before any PET procedures are initiated)
- Treatment with an investigational drug, device or other intervention within 30 days of study enrollment
- Anything that would place the individual at increased risk or preclude the individual's full compliance with or completion of the study (e.g., medical condition, laboratory finding, physical exam finding, logistical complication).

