5.5 Subject Withdrawal

5.5.1 *Reasons for Withdrawal*

Subjects are free to withdraw from participation in the study at any time upon request. An investigator may terminate a study subject's participation in the study if:

- Any clinical adverse event (AE), laboratory abnormality, or other medical condition or situation occurs such that continued participation in the study would not be in the best interest of the subject.
- The subject meets an exclusion criterion (either newly developed or not previously recognized) that precludes further study participation.

5.5.2 *Handling of Subject Withdrawals or Subject Discontinuation of Study Intervention*

Subjects wishing to withdraw from the study at any time may do so and should notify the study team. For payment to these subjects, see Section 5.3.

Withdrawals need not be replaced, but may be on a case-by-case basis, at the PI's discretion. The power calculations allow for a 20% dropout rate.

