7.2 TMD Patients

Prescreening (Study Week -8)

Chronic TMD subjects interested in the study will be prescreened via a phone interview using an IRB-approved checklist.

Screening
(*Study Week -3*)

The activities assigned to the Screening Visit will be completed within 3 weeks prior to the first session of Week 1. Following the informed consent process, subjects will undergo a baseline assessment and the completion of questionnaires, as listed in the study schedule (Table 2). The baseline visit will include a medical/dental history with limited physical that involves clinician assessed DC/TMD (Diagnostic Criteria/Temporomandibular Disorder) status. Also covered are a comprehensive medication history (6 months) and a review of eligibility.

Baseline PET/MRI
(*Study Week -1*)

Within 7 days preceding randomization and the first study treatment, subjects will undergo an MRI, as well as a PET scan that uses an [¹¹C]carfentanil radioligand, with a masseter muscle pain challenge via a 5% hypertonic saline intramuscular infusion. Pain questionnaires will also be completed during this visit window. All procedures are targeted for the week prior to HD-tDCS; however, due to occasional scheduling difficulties, they may be completed within 14 days prior to Day 1 of HD-tDCS. Completion of all procedures may require more than one clinic visit.

Treatment HD-tDCS
(*Study Weeks 1 through 2*)

Beginning at Day 1 of HD-tDCS, subjects will be randomized to active treatment or sham procedure. They will then attend 10 sessions, 1 each weekday (Monday through Friday) over a 2-week period, and will receive either the M1 HD-tDCS treatment or the sham treatment, preceded and followed by questionnaires. Missed days can be doubled and/or rescheduled within the 2-week schedule, as necessary, with study team approval.

Follow-up PET
Follow-up MRI &
First Follow-up Visit
(*Study Week 3*)

Within 7 days following the last study treatment, subjects will undergo an MRI as well as a PET scan that uses an [¹¹C]carfentanil radioligand with a masseter muscle pain challenge via a 5% hypertonic saline intramuscular infusion. Pain questionnaires will also be completed during this visit window. All procedures are targeted for the week following completion of HD-tDCS; however, due to occasional scheduling difficulties, they may be completed within 14 days following Day 10 of HD-tDCS. Completion of all procedures may require more than one clinic visit.

Follow-Up #2 & #3
(Study Weeks 6 and 10)

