Pain questionnaires will be completed again at 4 weeks (Follow-Up #2) and 8 weeks (Follow-Up #3) after the final treatment day (Study Weeks 6 and 10, respectively).

Table 2

SCHEDULE OF EVENTS – I. Procedures

Procedures	Phone PreScreening	Screening	PET/MRI #1 (Baseline) ^{1,2}	HD-tDCS #1-10 ⁸	PET/MRI #2/ Follow-up #1 ^{1,2}	Follow-up #2	Follow-up #3	Early Termination ³
Visit	P	1	2	3A-J	4	5	6	ET
Study Week	-8	-3	-1	1 – 2	3	6 (1 mth)	10 (2 mths)	N/A
Prescreening Script/Checklist	X ⁵							
Informed Consent		X ⁵						
Adverse Events		X ⁵	X ⁵	X	X	X	X	X
Medical/Dental History and Physical		X ⁵						
Medication History/ Concomitant Medications		X ⁵	X ⁵	X	X	X	X	
Quantitative Sensory Testing (QST)			X ⁵		X			
Eligibility Assessment ⁴		X ⁵						
PET Scan 
 Pregnancy Test (Dip)⁷ Drug Screen⁷ Blood sample for biomarkers Masseteric Pain Challenge (5% hypertonic saline) 			X ⁵		X			
Blood sample for genetic testing			X ⁵					
MRI Scan			X ⁵		X			
RANDOMIZATION				Week 1				
HD-tDCS (M-F for 2 weeks)				X ⁶				

¹ Target dates for PET/MRI are the week prior to Day 1 HD-tDCS session (Baseline) and the week after completion of HD-tDCS sessions (Follow-up); an additional week window is allowed to account for scheduling issues.

² Procedures may require more than one clinic visit.

³ Applicable if subject completes an in-person visit.

⁴ If subject is deemed eligible, schedule subject visits and provide subject with instructions for PET & MRI.

⁵ Healthy Volunteer subjects complete only these procedures indicated.

⁶ Missed days can be doubled in the (M-F) x 2 schedule, with study team approval. See Section 7.

⁷ Completed within 24 hours prior to PET session

⁸ HD-tDCS sessions will be scheduled M-F. See Section 7.2.

Table 2
SCHEDULE OF EVENTS – II. Questionnaires

Questionnaires	Phone PreScreening	Screening	PET/MRI #1 (Baseline) ^{1,2}	HD-tDCS #1-10 ⁸	PET/MRI #2/ Follow Up#1 ^{1,2}	Follow Up #2	Follow Up #3	Early Termination ³
Visit	P	1	2	3A-J	4	5	6	ET
Study Week	-8	-3	-1	1 – 2	3	6 (1 mth)	10 (2 mths)	N/A
Demographics		X ⁷						
Beck Depression Inventory		X ⁷						
DC/TMD Examination Form		X ⁷				X	X	
Expectation of Effect VAS		X						
McGill Pain Questionnaire (MPQ) (Long Form)		X						
MPQ (Short Form) ⁶		X	X	X	X	X	X	
Positive and Negative Affect Schedule (PANAS) ⁶		X ⁷	X ⁷	X	X	X	X	
GeoPain (via mobile device) ⁶		X	X	X	X	X	X	
Visual Analog Scale (VAS) ⁶		X	X	X	X	X	X	
Graded Chronic Pain Scale		X			X	X	X	

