applied to the co-registered BP_{ND} scans of the same image set. The MR scans are then anatomically standardized to ICBM brain atlas stereotactic coordinates by non-linear warping, and the resulting transformation matrix applied to both K₁ ratio and BP_{ND} image sets^{47, 48, 49, 50}. As an alternative approach for Aim3, ¹H-MRS spectra will be collected from the ACC (3x2x3cm) based on our prior work showing Glx alterations in this region following tDCS therapy. Single-voxel point resolved spectroscopy (PRESS)(TR/TE=2000/35ms) will be performed using 'VAPOR' water suppression with 32 averages to measure Glx and NAA levels. A MEGAPRESS experiment, which edits out the overlapping creatine peak at 3.0ppm will measure GABA levels⁵¹. The MEGA-PRESS experiment will use: TE=68ms (TE₁=15ms/TE₂=53ms); TR=1.8s; 256 transients of 2k datapoints; spectral width=2kHz; frequency selective editing pulses (14ms) applied at 1.9ppm (ON) and 7.46ppm (OFF).

8.1.4 *Questionnaires*

To assess the primary effectiveness endpoint, clinical pain intensity at rest will be measured using the VAS at study visits shown in Table 2, Schedule of Events – II. Questionnaires. Other questionnaires listed in Table 2 will be used to address the secondary objectives of the study.

8.2 *Laboratory Procedures/Evaluations*

8.2.1 *Clinical Laboratory Evaluations*

Pregnancy and urine drug screen testing will be performed by dipstick analysis to assess eligibility criteria prior to PET scans #1 and #2.

8.2.2 *Blood Samples for Study-Specific Analyses*

If the subject consents to participate in this part of the study, serial blood samples that do not exceed a total of 45 mL (3 Tbsp) will be collected during each PET scan for analysis of inflammatory biomarkers. This blood will be collected from a separate intravenous line placed into the vein of the arm that is opposite the arm used for the tracer injection. Approximately 6 mL (0.4 Tbsp) of blood will be drawn during each PET scan at time 0, 20, 45, 65 and 80 for analysis of biomarkers. See details in MOP Section 6.6.3. The blood samples will be frozen for future testing to look at biological substances in the blood and potential hereditary traits associated with migraine.

One additional, individual collection for genetic analysis will be performed for future studies. The blood for genetic analysis will be collected prior to tracer administration and will not exceed 25 mL (2.4 Tbsp) per scan.

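### A failed drug or pregnancy test at PET #2 is written as a study exclusion after randomisation, so a treated subject can be lost before the Week 6 primary endpoint

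*Combined protocol and SAP*

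**What the plan says.** Section 5.2 opens its list with "An individual who meets any of the following criteria will be excluded from participation in this study". The consequence is thus exclusion from the study, not only from a scan. Two items on the list are tied to the PET visits: "Drug test positive for opioid or recreational drug (e.g., cannabis) at the time of the PET scan visits" and "Pregnant or lactating (negative urine pregnancy test must be available before any PET procedures are initiated". Section 8.2.1 says which scans are meant: "Pregnancy and urine drug screen testing will be performed by dipstick analysis to assess eligibility criteria prior to PET scans #1 and #2".

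On timing, Section 7.2 states "Beginning at Day 1 of HD-tDCS, subjects will be randomized to active treatment or sham procedure". PET #2 is targeted for the week after the last session (Study Week 3), and the PET #2 procedures have some leeway: "they may be completed within 14 days following Day 10 of HD-tDCS".

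Section 5.5.1 says the investigator may end participation when "The subject meets an exclusion criterion (either newly developed or not previously recognized) that precludes further study participation".

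The primary endpoint (Section 3.2.1) is the change in clinical VAS from Screening to Follow-Up #2. Of that visit and the next, Section 7.2 says "Pain questionnaires will be completed again at 4 weeks (Follow-Up #2) and 8 weeks (Follow-Up #3) after the final treatment day". Table 2 shows no PET, pregnancy test or drug screen at either.

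**The concern.** At PET #1 these tests do ordinary screening work, because nobody has yet been randomised. At PET #2 the same wording acts on people who have been allocated and have finished treatment. If a failed test ends participation there, a randomised subject leaves the trial because of something that happened after allocation, and the Week 6 VAS is lost although collecting it does not depend on the scan.

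A positive opioid or cannabis test may also be related to pain. The population has pain not adequately controlled by earlier therapies (Section 5.1), and a subject whose pain has not improved may be more likely to have taken something for it. Removal could then depend on the outcome and occur at different rates in the two arms, which would distort the comparison that randomisation is meant to protect. Pregnancy adds to the lost data, but the documents give no reason to link it to pain.

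**Working it through.** **Sequence for a TMD subject**

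1. Weeks 1-2: randomisation on Day 1, then 10 sessions (Section 7.2).
2. Week 3: PET #2, at the latest 14 days after Day 10, with both dipsticks done within 24 hours before the scan (Table 2, procedures footnote 7) and described as eligibility tests (Section 8.2.1).
3. Week 6: primary VAS, 4 weeks (28 days) after the final session. Even the latest permitted PET #2 precedes it by 28 - 14 = 14 days.

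A subject terminated under Section 5.5.1 goes to the withdrawal visit of Section 7.3, which records adverse events and gives final instructions. The VAS row of Table 2 has no mark under Early Termination. No section says that a subject who fails a PET #2 test misses only the scan.

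**Where the text disagrees with itself**

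- Table 2 marks Eligibility Assessment at Screening only, whereas Section 8.2.1 places eligibility testing at both scans.
- Section 5.2 makes exclusion mandatory, whereas Section 5.5.1 makes termination optional.
- The population called intent-to-treat (Section 12) requires at least one set of post-treatment assessments. A set is not defined, so it is unclear whether a subject removed at PET #2 would be in it.

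**Possible shift in an arm mean**

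Assumptions, none of them from the documents: normally distributed change scores, removal of a fraction q in the sham arm only, and an SD of 2 VAS points. If those removed are exactly the worst outcomes, the mean of those remaining shifts by φ(z₁₋q)/(1 - q) SD. If removal follows a marker with correlation ρ to outcome (bivariate normal), the shift is multiplied by ρ.

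| q | Subjects of 30 | Shift, exactly the worst removed | Shift, ρ = 0.3 |
|---|---|---|---|
| 5% | 1.5 | 0.109 SD (0.22 points) | 0.3 × 0.109 = 0.03 SD (0.07 points) |
| 10% | 3 | 0.195 SD (0.39 points) | 0.3 × 0.195 = 0.06 SD (0.12 points) |

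Equal removal of the same kind in both arms leaves the difference in means unbiased and costs 3 to 6 of 60 primary outcomes.

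**Effect on power**

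The plan's dropout step reproduces: 24/(1 - 0.20) = 30 per group (Section 12.2). Its power statement does not, if the effect size of 1.2 is standardised: 24 per group then gives 98.3% power by the exact t-test, while 80% power at 24 per group corresponds to d = 0.826. That is a separate issue, so both values are carried. With f the assumed share removed at PET #2 beyond the planned dropout, n per arm = 30 × 0.8 × (1 - f).

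| f | n per arm | Power, d = 0.826 | Power, d = 1.2 |
|---|---|---|---|
| 0% | 24.0 | 80.0% | 98.3% |
| 5% | 22.8 | 77.9% | 97.7% |
| 10% | 21.6 | 75.5% | 97.1% |
| 15% | 20.4 | 73.0% | 96.2% |
| 20% | 19.2 | 70.3% | 95.1% |

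**The case against.** A reader might infer that a failed PET #2 test removes the subject automatically. The documents do not go that far. Section 5.5.1 is permissive and covers only a criterion that rules out further participation, which a positive dipstick need not do when only questionnaires remain. Section 2.3.7 allows a repeat drug test. Both points stand and limit the claim to a possible loss. They do not settle a confirmed positive, and leaving the decision to case-by-case discretion allows like subjects to be handled differently.

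A reader might also infer a known bias toward no effect of 0.11-0.19 SD. That figure requires every removal to fall in the sham arm and exactly on the worst outcomes. Subjects had taken no opioid pain medication in the past 3 months at entry and are screened at PET #1, so failures at PET #2 may be few. Section 12.3.2.1 describes a mixed model with time, and VAS is taken before and after the sessions and scans (Table 2, questionnaires footnote 6). A likelihood-based analysis could use those values and reduce bias where removal is predicted by pain already observed. The Week 6 value would still be missing, and Section 12.4 leaves the final analysis to a separate plan.

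Finally, it is tempting to say that drug use matters only for the scan. It does not. Section 5.1 requires stable pain medication before screening and no new TMD medication during the study, and opioid or cannabis use could itself lower the Week 6 VAS. Keeping such subjects could therefore also make sham look better. This does not justify dropping them, but it does call for a stated way of handling drug use in the analysis.

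**Conclusion.** The concern holds as a gap in the rules. Read together, Sections 5.2, 5.5.1 and 8.2.1 allow a randomised, fully treated subject to be removed in Week 3 for failing a test tied to the scan, and the primary outcome three weeks later is then not collected. This rests on the text alone.

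The statistical consequence is less certain. The documents give no failure rate at PET #2, no link between test result and pain, and no split by arm, so neither size nor direction can be stated. Under the assumptions shown, 0.11-0.19 SD is an extreme bound, and about 0.03-0.06 SD follows from a correlation of 0.3. Removal of 5-20% beyond planned dropout would take power from 80% to 78-70% at d = 0.826, or from 98% to 98-95% at d = 1.2. The main issue is avoidable, possibly outcome-related loss of primary data in a trial of 60. It should be corrected, but it does not undermine the design.

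**What to change.** Reconcile Sections 5.2, 5.5.1 and 8.2.1 and Table 2 so that:

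- the drug and pregnancy tests count as study eligibility criteria only before randomisation;
- a failed test at PET #2 does not by itself end the pain questionnaires already scheduled at Follow-Up #1 to #3;
- such a subject stays in the primary analysis as randomised.

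What a failed test means for the scan itself, and what follows from any other newly met exclusion criterion, should be left to the sponsor's clinical and PET safety rules. The consequence of a positive drug test for PET #2 needs its own statement, because no section other than 5.2 and 8.2.1 visibly gives one.

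Record opioid and cannabis use from the concomitant medication review already scheduled at each follow-up, and specify a sensitivity analysis of the primary endpoint that accounts for it.

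The cost is wording and one additional analysis, with no new visits or instruments. The downside is that some subjects will have a primary outcome but no PET #2 data, so the imaging analyses will rest on fewer subjects than the primary one.

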5.3 Strategies for Recruitment and Retention

We will recruit 60 chronic TMD pain patients divided into 2 groups: 30 for the active M1 HD-tDCS group and 30 for the sham HD-tDCS group. We will also include a total of 30

healthy volunteer subjects between the following two groups, if they are gender and age-matched to the active M1 HD-tDCS group:

1. We will use the PET/MRI data from up to 12 healthy controls and 12 TMD patients who were recruited and scanned during the NIDCR-NIHR56 DE022637 project.
2. We will recruit the balance of the healthy volunteer population, for a total of 30 subjects as detailed below.

Recruited patients will be screened from the UMhealthresearch.org recruitment network and the TMD and Orofacial Pain Clinic at the University of Michigan (from which ~90% of the 1,572 patients report TMD pain). In addition to active referral from these centers and others, advertisements will be placed in other pain clinics in the region. In-hospital advertisements will be placed in other departments at the institution, as well as across the university.

Subjects recruited will be prescreened by phone using an initial IRB-approved questionnaire. Those who pass the phone screening will be scheduled for an in-person screening visit, which will commence with a verbal and written informed consent process. Once informed consent has been obtained, subjects will undergo further screening; those subjects who are determined to be eligible to enter the study will be enrolled into either the TMD or healthy volunteer pools.

Study duration is expected to be approximately 3 months for each TMD patient; up to 10 weeks for healthy volunteers. Due to the repeated scheduling of PET and MRI visits, reminders (eg, phone and/or email; subject preference) may be implemented to help with retention.

During the course of participation, subjects will be compensated according to amounts stated in the informed consent form and approved by the IRB (Table 1). Subjects will be paid for visits completed until they finish the study or withdraw. Allowance for travel expenses may be provided in very specific situations when needed, and will be decided on case-by-case basis.

Table 1. Subject Compensation

VISIT NAME	NUMBER of Visits	COMPENSATION
Screening	1	\$25
PET #1	1	\$100
MRI #1	1	\$50
HD-tDCS Session	10 Planned	\$25 x 10 = \$250
PET #2	1	\$100
MRI #2	1	\$50
Follow-Up @ 1 Wk**	1	\$25
Follow-Up @ 1 Mo	1	\$25
Follow-Up @ 2 Mo	1	\$25
TOTAL		\$650
*\$175 for Healthy Volunteers		
*Healthy Volunteers will have completed the protocol after PET/MRI #1.		
**Follow-Up @ 1 Wk is during the week following the final HD-tDCS session.		

5.4 Treatment Assignment Procedures

5.4.1 *Randomization Procedures*

Participants initially will be screened by phone. After clinical exam and diagnosis of the DC/TMD Axis I Group, participants will be randomized to the treatment HD-tDCS or sham groups using the Taves covariate adaptive randomization method³⁸. Using this method, a new participant will be sequentially assigned to a group based upon the previous assignments of other participants and certain covariates³⁹. The first eight TMD participants will be randomized by coin flip and the remaining TMD participants will be randomized by age and gender, following the Taves covariate adaptive randomization protocol.

5.4.2 *Masking Procedures*

The PI, Co-Investigator, and any members of the research staff who will be analyzing study data (with the exception of the coordinator[s]/biostatistician) will be masked to participant treatment. The research coordinator and any study staff who will be NOT involved in the treatment of the study participants in the HD-tDCS study component will be unmasked in order to promptly address any emergency directly or indirectly associated with the procedure for safety reasons. The research coordinators are not masked, and thus are able to blind the machines prior to administration of the stimuli. The biostatistician transmits the code to the coordinator in a manner that keeps the investigators and co-I's blinded. Patients will be allowed to know the type of stimulation they received, active or sham, at the end of the study if requested.

